9.6.2 Prohibited Medication/Therapy

Treatment with the following concomitant medications/therapies is prohibited during the study unless otherwise specified in [Table 3](#). “As needed” (PRN) use of TCS or TCI is not permitted.

Table 3: Prohibited Medication/Therapy and Timeframe Prior to Baseline

Treatment(s)	Timeframe	
	Before Baseline/Day 1	Day 1 – Week 24
Coal tar products	2 weeks	Prohibited
Topical PDE-4 inhibitor	2 weeks	Prohibited
TCI, only for subjects not using stable TCI therapy \geq 14 days prior to baseline	2 weeks	Prohibited*
High- or very high-potency TCS (Class I-II according to the US classification) ² (applies to all subjects); any TCS only for subjects not using stable TCS therapy \geq 14 days prior to baseline	2 weeks	Prohibited*
Topical medications, including TCS/TCI, with occlusive dressings (eg, wet wraps)	2 weeks	Prohibited
Systemic corticosteroids (corticosteroid inhalers are permitted)	4 weeks	Prohibited
Phototherapy	4 weeks	Prohibited*
Tanning bed use	4 weeks	Prohibited
Immunosuppressive or immunomodulatory drugs (eg, cyclosporine A, oral tacrolimus, cyclophosphamide, azathioprine, methotrexate, mycophenolate mofetil)	4 weeks or 5 half-lives (whichever is longer)	Prohibited
Biologics and their biosimilars (eg, dupilumab, etanercept, adalimumab, infliximab, omalizumab, etc)	8 weeks or 5 half-lives (whichever is longer)	Prohibited
Investigational topical and systemic medication (eg, topical or oral JAK inhibitors)	8 weeks or 5 half-lives (whichever is longer)	Prohibited
Drugs with a sedative effect such as benzodiazepines, imidazopyridines, barbiturates, or sedative anti-depressants (eg, amitriptyline), except if these treatments were taken at a stable dose for at least 3 months before screening (Stable treatment with antihistamines with sedative effect, SSRIs, or SNRIs is allowed.)	1 week	Prohibited
Gabapentinoids (eg, gabapentin, pregabalin)	4 weeks	Prohibited
Cannabinoids	2 weeks	Prohibited
Alternative medicine for AD (eg, traditional Chinese medicine)	2 weeks	Prohibited
Live (attenuated) vaccines	12 weeks	Prohibited
Non-live vaccines, except vaccines specifically administered in the study (exceptions apply; see Section 9.6.1)	12 weeks	Prohibited

This document is confidential.

Abbreviation(s): AD=atopic dermatitis; JAK=Janus kinase; PDE-4=phosphodiesterase-4; SNRI=serotonin-norepinephrine reuptake inhibitor; SSRI=selective serotonin reuptake inhibitor; TCI=topical calcineurin inhibitor; TCS=topical corticosteroid.

* Unless used as rescue therapy

Note: These treatments should not be discontinued for reasons related to this clinical study.

If a prohibited therapy becomes necessary for the safety of the subject, the investigator should notify the medical monitor and discuss possible alternatives. If a subject receives a prohibited therapy during the clinical study (eg, inadvertent short-term use), the investigator should also notify the medical monitor and discuss whether or not it is acceptable for the subject to continue receiving the study drug.

Vaccinations during the study and follow-up period are not permitted, except for use of vaccines specifically administered in this study (ie, Tdap, MCV4) and non-live vaccines specified in Section 9.6.1.

9.6.3 Product Technical Complaints

All DCS and vaccine units must be inspected prior to preparation/injection by the persons performing the preparation/injection to ensure absence of visual defects that could lead to a DCS or vaccine PTC. This also includes the DCS plunger rod. In case of doubt, the DCS or vaccine should not be used, and the deficiency must be reported as defined in the pharmacy manual.

All PTCs should be reported to the sponsor/designee by filing the relevant forms available in the Investigator Site File and the pharmacy manual and as required by local regulations.

Refer to the current version of the pharmacy manual for further details.

9.7 Duration of Subject Participation

The expected duration for each subject's participation in the study is up to 28 weeks, including a 2- to 4-week screening period, a 16-week treatment period, and an 8-week follow-up period (12 weeks after the last study medication injection).

This document is confidential.

Page 67 of 133

The 12-week follow-up visit is not required for subjects who will continue in the LTE study (Protocol 118163).

9.7.1 Early Termination Visit

Subjects may discontinue from the study or discontinue the study treatment only and continue to participate in the study.

Subjects who prematurely discontinue from the study should undergo final study assessments according to the following guidelines:

- Subjects discontinued from the study during the treatment period on/before the Week 16 visit should attend an early termination visit.
- A follow-up/final visit is required 12 weeks after the last study drug administration.

Subjects who prematurely discontinue the study drug will be asked to continue participation in the study; however, subjects who discontinue the study drug prior to Week 12 should not be vaccinated. Subjects will be asked to return for all remaining visits and assessments (including daily assessment of pruritus, sleep disturbance, etc). Participation will continue until the subject completes the final study visit or otherwise discontinues study participation.

9.7.2 Unscheduled Visit

The subject should be reminded to adhere to the study schedule. Unscheduled visits are defined as visits to repeat testing for abnormal laboratory results, for follow-up of AEs, or to conduct efficacy assessments for subjects requiring rescue medication between regularly scheduled study visits. Visits occurring outside of the visit window are not considered unscheduled visits.

Assessments to be conducted at the unscheduled visit will depend on the reason for the visit: Any of the procedures/assessments listed in [Table 4](#) may be conducted, but not all are required. However, blood sample collection for [CCI](#) [REDACTED] are required during unscheduled visits that are conducted for safety reasons.

This document is confidential.

10 STUDY PROCEDURES

A written, signed ICF, assent form, and Health Insurance Portability and Accountability Act (HIPAA) authorization is required before any study-related procedures are performed.

Upon provision of the signed ICF/assent form, each subject will be assigned a unique SIN. For the duration of the entire clinical study, the subject will be identified using the SIN in all documentations and discussion.

The planned study assessments are in [Table 4](#). At each visit, assessments/procedures should be performed in the following order:

1. Patient-reported safety measurements
2. Investigator assessments (including efficacy and safety)
 - Electrocardiogram (ECG) should be done before vital signs measurements and blood draws (see Section [13.7](#)).
3. Sample collections for laboratory assessments
4. Sample collections for correlative assessments (PK, [CCI](#) [REDACTED] vaccine response)
5. Administration of study drug injections and vaccines

[figure not shown]
This document is confidential.

Page 69 of 133

Galderma S.A./Galderma R&D, LLC
Nemolizumab (CD14152)

RD.06.SPR.118380
Version 4.0

CCI

[figure not shown]

This document is confidential.

Galderma S.A./Galderma R&D, LLC
Nemolizumab (CD14152)

RD.06.SPR.118380
Version 4.0

CCI

[figure not shown]

This document is confidential.

Galderma S.A./Galderma R&D, LLC
Nemolizumab (CD14152)

RD.06.SPR.118380
Version 4.0

CCI

[figure not shown]
This document is confidential.

Page 72 of 133

Galderma S.A./Galderma R&D, LLC
Nemolizumab (CD14152)

RD.06.SPR.118380
Version 4.0

CCI

This document is confidential.

Page 73 of 133

11 IMMUNOGENICITY ASSESSMENTS

11.1 Vaccine Response

Humoral immune responses to tetanus and meningococcal vaccination will be determined using serum samples collected from all subjects according to [Table 4](#).

[figure not shown]
11.1.1 Tetanus Toxoid IgG Antibody Concentration

Serum concentrations of anti-tetanus IgG will be assessed. The detection and characterization of antibodies to tetanus toxoid will be performed using a validated immunoassay.

11.1.2 Meningococcal Serogroup C SBA Reciprocal Titer

Immune response to meningococcal vaccination will be determined by measuring functional antibody responses using an SBA assay.

CCI

[figure not shown]
This document is confidential.

Page 74 of 133

12 EFFICACY ASSESSMENTS

Efficacy measurements should be conducted by the investigators (or trained designees) and subjects (for patient-reported efficacy measurements) according to [Table 4](#).

Whenever possible, the same evaluator should make the assessment throughout the study.

[figure not shown]
This document is confidential.

Page 75 of 133

CCI

CCI

13 SAFETY ASSESSMENTS

Safety assessments will be conducted for all subjects at the screening visit (upon signing of the ICF) and at every subsequent visit.

13.1 Adverse Events

Adverse Event Definition

An AE is defined as any untoward medical occurrence in a clinical study subject administered a medicinal product which does not necessarily have a causal relationship with this treatment. An AE can therefore be any unfavorable and unintended sign (including an abnormal laboratory finding), symptom, or disease temporally associated with the use of a medicinal (investigational) product, whether or not it is related to the medicinal (investigational) product. This includes an exacerbation of preexisting conditions or events, intercurrent illnesses, drug interaction, or the significant worsening of the indication under investigation that is not recorded elsewhere in the eCRF under specific efficacy assessments.

Note(s):

- Any new sign or symptom reported by the subject that appears after accidental or intentional overdose or misuse should be reported as an AE.
- Whenever possible, a diagnosis should be reported on the AE form, instead of signs, symptoms, or abnormal laboratory values.
- Pregnancy is not to be considered an AE; however, it must be monitored and reported as described in Section 13.1.5.
- Each worsening of a chronic disease from the screening visit should be reported as a new AE.

The investigator or designee will report all AEs that occur from the time the ICF is signed until the end of the study. The sponsor/CRO should be informed if the investigator becomes aware of any safety information that appears to be drug-related, even after the subject has completed the clinical study.

This document is confidential.

Page 78 of 133

At each post enrollment visit, the investigator (or sub-investigator) will question the subject about AEs using an open non persuasive question to elicit reporting of AEs (for example, “Have you noticed any change in your health since the last visit?”). Directed questioning and examination will then be performed as appropriate.

Any AE occurring during the AE reporting period, whether it is related to the study drug(s) or not, will be recorded immediately in the source document and described on the Adverse Event Form (“AE Form”) along with the date of onset, severity, relationship to the study drug(s), and outcome, without omitting any requested and known information. Additional information will be requested under certain circumstances.

Adverse events assessed as related to the treatment or study procedure will be monitored until they have resolved or reached a stable condition. Other AEs will be monitored until the last visit if they have not resolved or reached a stable condition.

The investigator will obtain and maintain in the subject’s files all pertinent medical records, information and medical judgment from colleagues who assisted in the treatment and follow-up of the subject. If necessary, the investigator will contact the subject’s personal physician or hospital staff to obtain further details.

Assessment of Severity

Each AE will be assigned a category by the investigator as follows:

Mild: An AE that is easily tolerated by the subject, causes minimal discomfort, and does not interfere with everyday activities.

Moderate: An AE that is sufficiently discomforting to interfere with normal everyday activities; intervention may be needed.

Severe: An AE that prevents normal everyday activities; treatment or other intervention usually needed.

If there is a change in severity of an AE, it must be recorded as a separate event.

Assessment of Causality

The investigator is to determine whether there is a reasonable causal relationship between the occurrence of the AE, and exposure to the study drug (ie, nemolizumab or placebo) and/or study procedure (eg, injection, topical background therapy, blood sample collection). Medical judgment should be used to determine the relationship, considering all relevant factors including the pattern of the reaction, temporal relationships, relevant medical history, and confounding factors such as co-medication or concurrent diseases.

The expression “reasonable causal relationship” is meant to convey in general that there are facts or arguments to suggest a causal relationship (International Council for Harmonisation [ICH] E2A, Section IIIA 1).

The relationship assessment for an AE is to be completed using the following definitions as a guideline for all AEs occurring during this clinical study:

Reasonable possibility:

According to the reporting investigator, there is a reasonable possibility (ie, suggestive evidence or arguments) that there is a causal relationship irrespective of the dose administered:

- Between the study drug (nemolizumab) and the AE, and/or
- Between the clinical study protocol procedure (eg, injection, topical background therapy, blood sample collection) and the AE

No Reasonable Possibility:

No suggestive evidence or arguments can be identified regarding a causal relationship between the study drug or the clinical study protocol procedure and the AE.

Action Taken

The investigator will describe the action taken in the appropriate section of the eCRF, as follows:

- None

This document is confidential.

- Study drug stopped
- Study drug temporarily interrupted
- Concomitant medication (any additions or discontinuations)
- Other, specify

Follow-up of Adverse Events

All investigators should follow-up with subjects with AEs until the event is resolved or until, in the opinion of the investigator, the event is stabilized or determined to be chronic. Details of AE resolution must be documented in the eCRF.

Subjects should be followed up for 12 weeks (\pm 5 days) after receiving the last dose of study drug, and any AEs that occur during this time should be reported according to the procedures outlined above.

Documentation and Reporting of Adverse Events

Adverse events should be reported and documented in accordance with the procedures outlined below. All AEs occurring during the study must be documented on the relevant eCRF pages. The following data should be documented for each AE:

- Description of the symptom event
- Classification of “serious” or “not serious”
- Severity
- Date of first occurrence and date of resolution (if applicable)
- Action taken
- Causal relationship
- Outcome of event (unknown, recovered, not yet recovered, recovered with sequelae, death [with date and cause reported])

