16.6 Safety Analysis

All safety analyses will be conducted on the SAF, by treatment group.

All reported AEs will be coded using the Medical Dictionary for Regulatory Activities (MedDRA), version 22.0 or later. The treatment-emergent period will be defined as the period of time from the first dose date of study treatment through 12 weeks (84 days) after the last dose of study treatment (ie, up to the follow-up visit for completers), or the date of rollover to the LTE study (SPR.118163), whichever is earlier. The incidence of TEAEs (events with onset dates on or after the start of the study drug), drug-related TEAEs, SAEs, TEAEs leading to study drug discontinuation and treatment-emergent AESIs will be included in incidence tables, summarized by System Organ Class (SOC) and Preferred Term (PT). Events with missing onset dates (and no data to suggest the

[figure not shown]
This document is confidential.

event stopped prior to study treatment start) will be included as treatment-emergent. The incidence of TEAEs by severity, counting multiple AEs under SOC and PT for a subject at the maximum severity will be presented. All AEs will be listed by subject, along with information regarding onset, duration, relationship and severity to study drug, action taken with study drug, treatment of event, and outcome.

Clinical laboratory data and vital signs will be summarized using descriptive statistics, including observed values and change from baseline values, as well as numbers of subjects with values outside limits of the normal range, including shifts from baseline at each time point.

Summary tables will be provided for 12-Lead ECG, Physical Examination (Full and Symptom-oriented), ACT, PEF, and Respiratory Exam, by treatment group and visit where appropriate. Listings will also be provided.

[figure not shown]
CCI

This document is confidential.

Page 106 of 133

CCI

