## 10.3. Adverse Events / Adverse Drug Reactions

Adverse events (AEs) will be coded using MedDRA Version 25.0.

Treatment-emergent AEs (TEAEs) is defined as AEs with an onset date on or after the first dose date of study treatment. Partially missing date will be handled using the algorithm described in Section 6.3. AE

related to study drug is defined as AE with a relationship to study drug reported as 'Reasonable Possibility' or missing.

Summary table for adverse events will include the number and percent of subjects and the numbers of events by treatment group and by System Organ Class (SOC) and Preferred Term (PT). SOC and PT within each SOC will be sorted by descending overall frequency. Subjects who have multiple events in the same SOC and the same PT within each SOC will be counted only once in the subject counts, but all events will be considered and presented (if applicable). For summary by maximum severity, subjects who experience multiple occurrences of an AE, the most severe category for each SOC and for each PT within each SOC will be considered in the summary.

The summary tables for following TEAEs will be presented:

- Overall Summary: summary of the number and percentage of subjects reporting TEAEs, TEAEs by
  maximum severity, serious TEAEs, study drug-related TEAEs, drug-related serious TEAE, study
  drug-related TEAEs by maximum severity, treatment-emergent AESI, Confirmed or suspected
  COVID-19 infection, TEAEs leading to study drug withdrawal, TEAEs leading to study drug
  interruption, TEAEs leading to study discontinuation, and TEAEs leading to death
- The total number and incidence of TEAEs by SOC and PT
- The total number and incidence of Serious TEAEs by SOC and PT
- The total number and incidence of TEAEs related to study drug by SOC and PT
- The total number and incidence of serious TEAEs related to study drug by SOC and PT
- The total number and incidence of TEAEs by SOC, PT, and maximum severity
- The total number and incidence of drug-related TEAEs by SOC, PT, and maximum severity
- The total number and incidence of TEAEs leading to temporary interruption of study drug by SOC and PT
- The total number and incidence of TEAEs leading to permanent discontinuation of study drug by SOC and PT
- The total number and incidence of TEAEs leading to study discontinuation by SOC and PT
- The total number and incidence of TEAEs of special interest by SOC and PT

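### Every change in AE severity becomes a separate event while TEAEs are defined by onset date alone, so event totals are inflated and AEs that begin in screening can be misclassified

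*Protocol*

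**What the plan says.** Four rules bear on this point.

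- **Collection.** Protocol 13.1: "The investigator or designee will report all AEs that occur from the time the ICF is signed until the end of the study". Screening lasts 2 to 4 weeks, so AEs that begin before the first dose are on the AE form.
- **Splitting.** Protocol 13.1, under the assessment of severity: "If there is a change in severity of an AE, it must be recorded as a separate event". It covers any change, up or down. By contrast, the same section's note on chronic disease is directional: there, only a worsening is reported as a new AE.
- **Classification.** SAP 10.3: "Treatment-emergent AEs (TEAEs) is defined as AEs with an onset date on or after the first dose date of study treatment". Protocol 16.6 applies the same onset test and adds a window, "the period of time from the first dose date of study treatment through 12 weeks (84 days) after the last dose of study treatment", cut short by rollover to the extension study. That window is also a date criterion. Neither document requires a pre-dose event to have worsened.
- **Counting.** SAP 10.3 says the AE summary tables "will include the number and percent of subjects and the numbers of events by treatment group". A subject with several events in one SOC and PT contributes one to the subject count, but every event stays in the event count. The maximum-severity tables take the most severe category per subject.

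The documents do not say what onset date a severity-change record carries. Protocol 13.1 asks for an onset date on the AE form and, in its documentation list, for the date each AE first occurred. No readable rule joins the records of one episode.

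**The concern.** The splitting rule was written for data capture, and the TEAE rule takes each captured record as a new event. Nothing between them recognises that two records may be one illness. Three consequences are possible.

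- Event totals count grade changes as well as illnesses, and the listed durations are broken into pieces.
- A recovering screening AE may appear as something that emerged on treatment.
- A screening AE that truly gets worse on treatment may not appear in the TEAE tables at all.

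Incidence and severity of AEs, including TEAEs, is the trial's stated safety endpoint. The last two errors reach subject incidence as well as event totals. The vaccine-response analyses are untouched.

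**Working it through.** The plan gives no figure to reproduce. The check applies the written rules to simple AE courses on the protocol's three-grade scale.

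**Rule for the count.** Let k be the number of grade changes on or after the first dose.

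- AE that starts on treatment: 1 + k TEAE records. This holds whichever date the later records carry, because both the original date and the change date are post-dose.
- AE that starts in screening: k TEAE records if each new record takes the date of change, and 0 if it keeps the original date.
- Sensible target: one event for an AE that starts on treatment. For a screening AE, one event if it worsens on or after the first dose and none otherwise.

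**Numbers put in.**

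| Course | k | TEAE events, change date | TEAE events, original date | Target |
|---|---|---|---|---|
| Starts on treatment: severe, moderate, mild | 2 | 1 + 2 = 3 | 1 + 2 = 3 | 1 |
| Starts in screening as moderate; mild after dosing | 1 | 1 | 0 | 0 |
| Starts in screening as severe; moderate, then mild after dosing | 2 | 2 | 0 | 0 |
| Starts in screening as mild; moderate after dosing | 1 | 1 | 0 | 1 |

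The change-date reading is wrong in the first three rows. The original-date reading is wrong in the first and last. Neither gives the target throughout.

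**Subject level.** In the first row the subject is counted once in the PT and shown as severe, which is correct; only the event total is wrong. In the second and third rows, under the change-date reading, the subject goes from 0 to 1 in that PT, and in the any-TEAE line too if there is no other TEAE. In the fourth row, under the original-date reading, the subject goes from 1 to 0 in that PT.

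**Trial level.** Under the change-date reading, the share of an arm that falsely gains any TEAE is q × r × u, where:

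- q is the share of subjects with an AE open at first dose;
- r is the share of those whose AE steps down a grade on treatment rather than simply resolving. A mild AE has no lower grade, so only moderate or severe AEs contribute;
- u is the share of those subjects with no other TEAE.

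None of the three is in the documents. If they are equal in the two arms, the false difference between arms is zero.

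**The case against.** **The onset date is not stated.** If the new record keeps the date of first occurrence, an improving pre-dose AE stays outside the TEAE tables. This is correct, and it means false TEAEs from recovering screening AEs cannot be asserted as certain. It does not clear the plan: that reading loses worsening of pre-dose AEs and leaves the inflated event totals in place. The loss is narrowed by the protocol's separate instructions to report worsening of chronic disease, and of clinically significant laboratory findings, as AEs. Those instructions do not settle the date for severity-change records in general.

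**The main tables are protected.** Subjects are counted once per SOC and PT, maximum severity is used, AE tables are descriptive, and all AEs are listed so that a split episode can be traced. This stands for AEs that start on treatment. It does not help with AEs that start in screening.

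**The error is conservative.** Over-counting cannot hide a signal in subject incidence. That is true only if the change date is used.

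**Other documents may hold the rule.** AE form instructions, the data management plan and the blind-review plan are not available here and may do so. Even so, the SAP defines what is tabulated and should state it.

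**A stronger inference about the arms.** A reader might infer that the active arm collects more spurious TEAEs because itch, sleep loss and skin complaints ease faster on nemolizumab. The documents do not support this. Protocol 13.1 makes the disease under study an AE only on significant worsening not captured by the efficacy assessments. Clinically significant screening findings on laboratory tests, vital signs and physical examination, and ECG abnormalities at screening, go to medical history. Subjects who receive rescue therapy in screening are ineligible. Baseline itch that improves therefore generally has no AE record to split. Any numerical difference between arms would come from assuming different improvement rates at the outset.

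**Conclusion.** The point holds as a conflict between the recording rule and the tabulation rule. Its size per episode is exact. An on-treatment AE with two grade changes counts as three events instead of one under either reading of the onset date. For an AE that begins in screening, the direction of the error depends on a date the documents leave open: one or two false TEAE events in the improving courses shown if the change date is used, or one missed TEAE in the worsening course if the original date is kept. Sites could also differ in which date they enter.

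The effect on the trial's totals cannot be computed from the documents, and no bias between arms is demonstrated. The conclusion assumes that sites follow the splitting rule as written and that no unseen instruction merges the records. It is worth correcting because the affected tables report the safety endpoint.

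**What to change.** In SAP 10.3:

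1. Define a TEAE as an AE that first starts, or worsens in severity, on or after the first dose. Name the reference for worsening; the grade current at first dose is the natural choice. Keep the protocol's end of window.
2. State that a record created only because an AE improved does not start a TEAE.
3. Link each severity-change record to its parent AE, on the AE form or at the blind data review that Protocol 16 already plans. Count linked records as one event at maximum post-dose severity. Take onset from the parent record, or from the date of worsening for an AE that began before the first dose.

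This gives the target count in all four courses above whichever date sites have entered as onset, provided the date of each severity change is recorded. Protocol 13.1 can keep its splitting rule, so the severity history is preserved.

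The cost is a linking field or a data-review step, a few SAP sentences and slightly more programming. Nothing further is asked of subjects.

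### Protocol 13.1 defines AE causality as drug and/or procedure, and SAP 10.3 uses the same answer to define drug-related TEAEs, so procedure-only events may be counted as drug-related

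*Protocol*

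**What the plan says.** Protocol 13.1 (Assessment of Causality) asks the investigator to judge whether an AE is linked to the study drug and/or a study procedure, and provides two answers.

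- *Reasonable possibility* has two limbs. The first is "Between the study drug (nemolizumab) and the AE, and/or". The second is "Between the clinical study protocol procedure (eg, injection, topical background therapy, blood sample collection) and the AE".
- *No Reasonable Possibility* is defined as follows: "No suggestive evidence or arguments can be identified regarding a causal relationship between the study drug or the clinical study protocol procedure and the AE".

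The relationship assessment is to be completed "using the following definitions as a guideline for all AEs occurring during this clinical study".

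On recording, an earlier paragraph of Protocol 13.1 says that each AE is described on the AE form "along with the date of onset, severity, relationship to the study drug(s), and outcome". The later list of data to document for each AE has a single "causal relationship" entry. Neither document names an item for relationship to a procedure.

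Under SAP 10.3, an AE "related to study drug is defined as AE with a relationship to study drug reported as 'Reasonable Possibility' or missing". This rule feeds the tables of drug-related TEAEs (14.3.1.3), drug-related serious TEAEs (14.3.1.5) and drug-related TEAEs by maximum severity (14.3.1.7), and the matching rows of the overall summary (14.3.1.1).

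**The concern.** The protocol's answer covers two causes, the drug or a procedure. The SAP attaches the same label to one cause, the drug. An event such as bruising after a blood draw, or local irritation from a background topical, may have nothing to do with nemolizumab or placebo. By the protocol's definitions it still qualifies for the answer that the SAP reads as drug-related.

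What is at stake is the meaning of the drug-related tables. Readers will take them as the investigators' view of what the study drug caused. If some entries reflect venepuncture or topical therapy, the incidences are too high. The comparison between arms may also shift, if such events are not equally frequent in the two arms. Sites could also score the same event differently, depending on whether they follow the drug-labelled form item or the drug-or-procedure definition.

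The point concerns procedures and topical background therapy. It does not concern attribution to the vaccines.

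**Working it through.** The plan states no AE rate and no figure for this point, so there is nothing to reproduce. The check sets the texts side by side and then asks what follows for the tables.

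**Step 1. Which answer fits a procedure-only AE?** Take an AE that the investigator attributes to blood sampling and not to study drug.

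| Protocol 13.1 answer | Condition | Met? |
|---|---|---|
| Reasonable possibility, limb 1 | link to study drug | no |
| Reasonable possibility, limb 2 | link to a protocol procedure | yes |
| Reasonable possibility overall | limb 1 and/or limb 2 | yes |
| No Reasonable Possibility | no link to drug or procedure | no |

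There is no third answer. The same result holds for an AE attributed only to topical background therapy, which the second limb names as an example.

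**Step 2. Where is the answer recorded?** The AE form item is described as relationship to study drug(s). The data list has one causality entry. The definitions in Step 1 are the only ones given and apply to all AEs. A drug-labelled item is therefore to be completed with a drug-or-procedure definition. These two parts of Protocol 13.1 do not agree, and the text does not say which governs.

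**Step 3. What does the SAP do with it?** SAP 10.3 tests whether the relationship to study drug is Reasonable Possibility or missing. It has no condition that sets aside procedure-only events. If such an event carries Reasonable Possibility in the field the SAP reads, it is counted as drug-related.

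**Step 4. What would that do to the tables?** For one arm, let p be the proportion of subjects with at least one AE classed as drug-related when the question is answered for the drug alone. Let r be the proportion with no such AE but at least one procedure-only AE entered as Reasonable Possibility. Then

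- reported drug-related proportion = p + r
- reported difference between arms = (p_nemolizumab − p_placebo) + (r_nemolizumab − r_placebo)

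The reported incidence is never below p. If r is equal in the two arms, the difference is unchanged and only the absolute levels rise. If r differs, the difference moves by r_nemolizumab − r_placebo, in either direction. Neither document gives p or r. Equal r cannot be assumed either, because Protocol 9.6.1.1 lets background therapy be tapered, stopped and restarted according to disease activity, so its use may differ by arm. If the eCRF has a drug-only field answered for the drug alone, r = 0 and the tables are correct as planned.

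**Step 5. Which outputs are touched?** Only those that use causality. The safety endpoint (Protocol 6.2.2.3, SAP 4.2.3) is the incidence and severity of AEs, including AESIs, TEAEs and SAEs, and does not depend on attribution.

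**The case against.** The strongest reply is that every place where the data are recorded or used names the study drug: the AE form item in Protocol 13.1, the derivation in SAP 10.3, and the AE listing described there. On that reading an investigator asked about relationship to study drug would answer no for a venepuncture bruise. The definitions are also called a guideline, to be applied with medical judgment. SAP 10.3 plans only counts and percentages for drug-related TEAEs, with no test, ratio or interval. Any over-attribution is conservative for the absolute incidence, as is the SAP's choice to count a missing relationship as related. A combined scale also has a legitimate use, since Protocol 13.1 sets follow-up for AEs related to the treatment or a study procedure.

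Much of this stands, and it limits the point. A reader might infer that the scale forces every procedure-only AE into the drug-related count. The documents do not support that: the definitions are guidance, the SAP condition is on the drug relationship, and the eCRF is not among the documents.

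The reply does not remove the conflict. The only definitions offered for the two answers are drug-or-procedure definitions, and they apply to all AEs. The label on the form item does not override them, and the SAP adopts the answer without qualification. A conservative direction for the absolute rate also says nothing about the comparison between arms.

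**Conclusion.** The internal conflict is real. Protocol 13.1 merges drug and procedure causality in one two-level answer, and SAP 10.3 uses that answer as if it concerned the drug alone. Applied literally, the definitions allow AEs attributed only to a procedure or to background therapy to be counted as drug-related.

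The consequence is possible but not shown. The drug-related tables may be overstated by an amount that the documents do not let anyone estimate, with an unknown balance between arms. The effect is zero if drug causality has its own eCRF field answered for the drug alone. A reader might also infer a definite inflation of drug-related TEAEs in both arms, or a set dilution of the contrast between them. Either would need procedure-only event rates by arm, which the documents do not give.

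The scope is narrow: Tables 14.3.1.3, 14.3.1.5 and 14.3.1.7 and the corresponding summary rows. The vaccine-response analyses and the TEAE, SAE and AESI tables that do not use causality are unaffected.

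**What to change.** 1. In Protocol 13.1, define and record two separate yes/no items for each AE: relationship to study drug, and relationship to study procedure or background therapy. The follow-up rule for AEs related to either can then refer to both items.
2. In SAP 10.3, state that only the study-drug item defines drug-related TEAEs.
3. If the eCRF already has two fields, leave it as it is, correct the two definitions in Protocol 13.1, and name in SAP 10.3 the field that the derivation uses.

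The cost is at most one eCRF item, a few sentences in the protocol and one phrase in the SAP. No table shell changes.
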